## 3.3.8. Definitions and Terminology

#### Baseline Value

Baseline will be defined as the last valid evaluation done before the study drug administration on Day 1. For ECG, the mean of the 3 triplicate ECG assessments (9 assessments) performed on Day -1 will serve as the Baseline value.

#### Day 1

Day 1 is the earliest day that study drug is first initiated.

#### Study Day

Study Day is defined relative to Day 1. Thus, the study day of an event is calculated as:

For events occurring on or after Day 1, Study Day = event date - date of Day 1 + 1.

For events occurring prior to Day 1, Study Day = event date – date of Day 1

## Scheduled Study Visit

Scheduled Study Visit is the nominal visit as recorded on the CRF.

## Derived Study Visit

Derived Study Visit is the visit designation reflective of when an actual study assessment was measured, as defined in Section 3.3.7. When compliance with the planned schedule of visits is good, the derived study visit will be the same as the scheduled study visit. The derived study visits re-classifies visits that occur off schedule.

#### Last Dose of Study Drug (Double-Blind Phase)

Last Dose of Study Drug (Double-Blind Phase) is defined as the last date a patient received study drug during the double-blind phase (up to Week 12).

### Last Dose of Study Drug (Open-Label Extension Phase)

Last Dose of Study Drug (Open-Label Extension Phase) is defined as the last date a patient received study drug through the end of the open label extension phase (up to Week 52). If a patient discontinued drug during the 12-week double-blind phase, the last dose of study drug for the open label extension would be the last dose of study drug in the double-blind phase.

## Days on Treatment

Days on treatment will be calculated as the number of days from the date of first dose to the date of last dose, inclusive. This will be calculated separately for the 12-week double blind phase as well as for the full study to include the open-label extension phase.

#### Treatment Compliance

Treatment compliance (%) during a specified period is defined as the total number of tablets taken by a patient during that time divided by the number of tablets prescribed during that time, multiplied by 100. The number of tablets prescribed during a specified period will be calculated by multiplying the number of days in that period by the number of tablets prescribed per day.

#### Change from Baseline

Change from Baseline for a given endpoint is defined as the Derived Study Visit X value minus the Baseline Value.

## PANSS and NSFS Response

PANSS and NSFS response are defined as experiencing a  $\geq$  30% decrease from Baseline in PANSS total score and NSFS score, respectively.

Additionally, the same analysis will be repeated using  $\geq 20\%$  decrease from Baseline in PANSS total score and NSFS score.

## Relapse

Relapse is defined as a patient early terminating from the study due to a treatment-emergent adverse event (TEAE) or early termination decision based on the adverse events and preferred terms in Table 2.

Table 2 Terms Defining Relapse

Adverse Event	Preferred Term	
Worsening of paranoid schizophrenia with symptom of agitation	Agitation	
Completed suicide by laying on the train tracks	Completed suicide	
Hallucination increase	Hallucination	
Worsening of mental status	Mental impairment	
Worsening of psychosis	Psychotic disorder	
Increase psychotic symptoms	Psychotic symptom	
Agitation and aggressivity inside schizophrenia	Schizophrenia	
Schizophrenia worsening	Schizophrenia	
Exacerbation of schizophrenia	Schizophrenia	
Schizophrenia relapse	Schizophrenia	

Additionally, disposition data will be examined for the identification of relapse in patients where an adverse event is not recorded as the cause of early termination from the study. Examples of such disposition data are comments such as: "Criterion #5 of study stopping rule", "worsening of psychotic symptoms", "Occurrence of dangerous behavior against self or others" or "Recurrence of positive symptoms".

Relapse will be defined in two ways: relapse in the Double-Blind phase, and relapse overall. Patients who are identified as possible cases of relapse will have their information recorded in a log which will undergo adjudication to confirm cases of relapse. For relapse in the Double-Blind phase, this adjudication will occur prior to unblinding of the Double-Blind phase. For all subsequent cases of relapse, this adjudication will occur prior to lock of the Open-Label extension phase.

#### Time to Relapse in Double-Blind Phase

Time to relapse in Double-Blind phase is defined as the number of days from Day 1 to the date of early termination in the Double-Blind phase due to relapse as defined above. If a patient is not

observed to have relapsed during the Double-Blind phase, he or she will be censored at the date of termination from or completion of the Double-Blind phase.

#### Time to Relapse in Study

Time to relapse in study is defined as the number of days from Day 1 to the date of early termination due to relapse as defined above. If a patient is not observed to have relapsed during the study, he or she will be censored at the date of termination from or completion of the study.

#### Adverse Event

An adverse event is any untoward medical occurrence in a clinical study patient administered a medicinal (investigational or non-investigational) product. An adverse event does not necessarily have a causal relationship with the treatment. An adverse event can therefore be any unfavorable and unintended sign (including an abnormal finding), symptom, or disease temporally associated with the use of a medicinal (investigational or non-investigational) product, whether related to that medicinal (investigational or non-investigational) product or not.

This includes any occurrence that is new in onset or aggravated in severity or frequency from the Baseline condition, or abnormal results of diagnostic procedures, including laboratory test abnormalities.

All adverse events will be recorded on the Adverse Event CRF.

## Treatment-emergent Adverse Event

Any recorded adverse event that occurs on or after the initiation of study treatment and less than or equal to 14 days after the last dose of treatment is considered treatment-emergent. Additionally, it is assumed that an adverse event which was reported to have started on Day 1 without an associated onset time may have occurred after the initiation study treatment. Hence, adverse events occurring on Day 1 without an onset time are assumed to be treatment emergent.

#### Adverse Event of Special Interest

Adverse events of special interest are any episode of palpitations or abnormal heart rhythms, dizziness or syncope, or an episode of seizure.

#### Serious Adverse Event (SAE)

An SAE is defined as any AE that results in any of the following:

- **Death**: The patient died as the result of the event.
- **Life-threatening event**: Any AE that places the patient, in the view of the Investigator or Sponsor, at immediate risk of death from the AE as it occurred, i.e., does not include an AE that had it occurred in a more severe form, might have caused death.
- Required or prolonged inpatient hospitalization: The AE resulted in hospitalization or
  prolonged an existing hospitalization. Since hospitalization may be part of the study, only
  hospitalizations that are longer than expected based on Investigator judgment, will be
  considered prolonged hospitalizations.
- **Persistent or significant disability/incapacity**: An AE that results in a substantial disruption of a person's ability to conduct normal life functions.

- Congenital anomaly/birth defect: A congenital anomaly/birth defect that occurs in the offspring of a patient exposed to the IP.
- Important medical events: An AE that may not result in death, be life-threatening, or require
  hospitalization may be considered an SAE when, based upon appropriate medical judgment,
  the event may jeopardize the patient and may require medical or surgical intervention to
  prevent one of the outcomes listed above.

## Concomitant Medications

Concomitant medications are those medications taken on or after the initiation of study treatment. This definition includes medications started prior to the initiation of study treatment but continuing concomitantly with study treatment.

#### Prior Medications

Prior medications are those medications taken and completed prior to the initiation of study treatment.

#### 3.4. TIMING OF ANALYSIS

Data from the double-blind 12-week phase are the primary focus of this study and will be analyzed once the last patient completes Visit 11 assessments (the Week 12 visit), the database through the double-blind phase has been cleaned and locked, and the treatments are unblinded.

A final analysis of the cumulative data through the open-label extension phase will be conducted once the last patient completes or discontinues the study, the resulting clinical database has been cleaned, quality checked, the final database lock has occurred, and the MIN-101 dosing arms are unblinded.

#### 4. ANALYSIS POPULATIONS

The populations for analysis will include the enrolled population, intent-to-treat population (ITT), the safety population (SAF), and the per-protocol population (PP).

#### 4.1. ENROLLED POPULATION

The enrolled population represents all patients that signed the informed consent form. This population is being used for presentation of subject disposition, as well as for all listings.

## 4.2. INTENT-TO-TREAT POPULATION (ITT)

The intent-to-treat population for this study is defined as all patients that were randomly assigned to study drug and received at least one dose of study drug. Patients in this population will be analyzed according to the treatment to which they were randomized, regardless of what treatment they received. All efficacy analyses will be based on this population and treatment assignment. In addition, Baseline patient characteristics and anthropomorphic measures will be based on this population.

## 4.3. SAFETY POPULATION (SAF)

The safety population is the population of all patients who were randomly assigned to study drug and received at least one dose of study treatment. Patients in this population will be analyzed according to the treatment they received, regardless of which treatment they were randomly assigned. All safety and tolerability analyses will be based on this population and treatment assignment.

## 4.4. PER-PROTOCOL POPULATION (PP)

The per-protocol population will include all patients in the ITT Population who do not present major protocol violations, i.e., violations thought to interfere with efficacy results such as erroneous diagnosis, insufficient compliance (< 75%), or intake of prohibited concomitant medication. Major protocol violations will be identified before breaking the randomisation code.

Patients' assignment to analysis sets will be performed during the pre-analysis review meeting while the data remain blinded.

All efficacy analyses will be performed on both the ITT and PP sets.

#### 5. STATISTICAL METHODS

Descriptive statistical methods will be used to summarize the data from this study, with hypothesis testing performed for selected endpoints. Unless stated otherwise, the term "descriptive statistics" refers to number of patients (n), mean, median, standard deviation (SD), minimum, and maximum for continuous data and frequencies and percentages for categorical data. All data collected during the study will be included in data listings. Unless otherwise noted, the data will be sorted by treatment group, patient number, and by date within each patient number.

The term 'treatment group' refers to the three treatment arms of this study: Placebo, 32 mg MIN-101, and 64 mg MIN-101.

All statistical testing will be two-sided and will be performed using a significance (alpha) level of 0.050 unless stated otherwise.

The statistical analyses will be conducted with the SAS® System version 9.4 or higher. All analyses will be performed using formal verification procedures. Specifically, results will be verified utilizing independent programming prior to issuance of the draft statistical report. All documents will be verified by the lead statistician to ensure accuracy and consistency of analyses.

# 5.1. PATIENT DISPOSITION, DEMOGRAPHIC AND BASELINE CHARACTERISTICS

Patient disposition will be presented for all patients. The number of patients who meet all eligibility criteria will be presented, as well as the number of patients included in the Enrolled, ITT, SAF, and PP populations. The number of patients who completed all study treatment or discontinued from the study will be provided.

The reasons for early study discontinuation will be presented by treatment group, for the study overall as well as separately within the double-blind and open label extension phases, by visit of discontinuation, and overall. Additionally, the number of days on study and within each study

phase will be summarized for all treated patients, as well as the frequency of patients in which the study blind was broken.

Demographic data, Baseline characteristics including age, weight, height, body mass index (BMI), gender, race, psychiatric and medical history, as well as efficacy parameters baseline scores will be summarized using descriptive statistics within the ITT and SAF populations, as appropriate, and will be presented by treatment group and overall. The number and percent of patients with a current or historical presence of abnormal finding in medical history excluding psychiatric disorders will be summarized by treatment group and overall. This information will be reviewed for Baseline differences, but no statistical testing will be performed.

Additionally, study treatment exposure and treatment compliance will be summarized by treatment group. The number of days on study treatment will be summarized for all treated patients. Treatment compliance over the double-blind and open label extension treatment periods will be similarly summarized by treatment group.

#### 5.2. EFFICACY ANALYSIS

The efficacy analyses will be based on the ITT Population, although they will also be performed for the PP population for comparison.

[figure not shown]
All efficacy parameters will be summarized descriptively by treatment arm and visit, as appropriate. All statistical tests will be 2-sided hypothesis tests performed at the 5% level of significance. All confidence intervals will be 2-sided 95% confidence intervals unless stated otherwise.

Additionally, by-visit analyses will be carried out for all efficacy parameters as deemed applicable using the mixed-effects model for repeated measures (MMRM).

Sensitivity analyses will be performed to better understand the impact of missing data and/or imputation of the primary efficacy endpoint, as described in Section 3.3.4.2.

#### Impact of Coronavirus Disease 2019 (COVID-19) Pandemic

The impact of the COVID-19 pandemic on the conduct and integrity of the study data will be evaluated by examining the efficacy (primary and key secondary endpoints) and safety data (treatment-emergent adverse event [TEAE], and select ECG parameters) for changes based on the date cutoff of 01 February 2020, and using descriptive summaries as appropriate.

Consequently, the analysis of the primary and key secondary endpoints for both the ITT and PP populations will be performed as planned above and will be repeated after excluding the site's data in full.

## 5.2.1. Primary Estimand

The primary estimand, the main clinical quantity of interest to be estimated in the study, is defined by the following components:

**Population**: Stable patients with schizophrenia with a predefined minimum PANSS negative symptom score before randomization.

**Endpoint**: Change in the PANSS Marder NSFS from Baseline to the end of Week 12.

The NSFS consists of the sum of the ratings (on a scale of 1-7, from least to highest severity of psychopathology) across the PANSS items N1, N2, N3, N4, N6, G7, and G16. Thus, each assessment is a number between 7 and 49.

N1. Blunted affect

N2. Emotional withdrawal

N3. Poor rapport

N4. Passive/apathetic social withdrawal

N6. Lack of spontaneity

G7. Motor retardation

G16. Active social avoidance

**Measure of Intervention**: The effect of the initially randomized treatment that would have been observed had all patients remained on their treatment throughout the double-blind phase.

**Intercurrent events**: Early study discontinuation for any reason.

**Summary measure**: Difference in treatment means.

#### 5.2.2. Primary Efficacy Analysis

As noted in Section 3.3.4, no imputation of data elements will be performed for the primary analysis to be submitted to the US FDA. Pattern-mixture modelling imputation of missing primary endpoint data will be performed before conducting the primary analysis to submit within the EMA dossier. In both approaches, the estimand and analytic approach of using MMRM to evaluate the potential treatment effects is the same, but the data used to analyze the estimand is different between the US FDA and EMA dossiers.

The PANSS Marder NSFS scores and change from Baseline will be summarized by treatment group and study visit. In addition, the trend in change from Baseline in Marder NSFS scores over the series of visit assessments will be presented graphically.

Change from Baseline to Week 12 in the PANSS Marder NSFS score will be analyzed using a MMRM with fixed effects for treatment group (MIN-101 64 mg, MIN-101 32 mg, and placebo), region, visit, and treatment-by-visit interaction, a random effect for patient within treatment group, and Baseline NSFS as covariate. An unstructured covariance matrix will be used to model the covariance of within-patient scores. The Kenward-Roger approximation will be used to estimate denominator degrees of freedom. Comparison against placebo will be performed with the MIN-101 64 mg and 32 mg doses.

The hypotheses can be expressed as follows:

```
Null Hypothesis (H_0): \muMIN-101 64 mg - \muControl = 0 and \muMIN-101 32 mg - \muControl = 0
```

Alternative Hypothesis (Ha):  $\mu$ MIN-101 64 mg -  $\mu$ Control  $\neq$  0 or  $\mu$ MIN-101 32 mg -  $\mu$ Control  $\neq$  0

where  $\mu$ MIN-101 64 mg and  $\mu$ MIN-101 32 mg refer to the mean change from Baseline to week 12 in the PANSS Marder NSFS score at each of the 2 experimental doses, and  $\mu$ Control refers to the mean change from Baseline to week 12 in the PANSS Marder NSFS score in the placebo arm.

As described in Section 3.3.3.1, the adjustment for multiplicity within the family of primary hypotheses will utilize the truncated Hochberg procedure for the purpose of reporting results. This procedure will allow the null hypothesis of no treatment difference for both the 64 mg and 32 mg doses versus placebo to be rejected if largest p-value of comparing either of these 2 doses versus placebo is at or below 0.05. Otherwise, the lowest of these 2 p-values must be at or below 0.025 reject the null hypothesis for the representative dose.

Three approaches will be used to assess the sensitivity of the primary endpoint to patterns of early withdrawals or missing data as described in Section 3.3.4.2. The sensitivity analyses will implement the same analytic approach using MMRM to evaluate potential treatment effects.

Finally, a cumulative distribution function for the change from Baseline to Week 12 in the PANSS Marder NSFS score will be presented.

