# 8.2.2. Efficacy Evaluations

Efficacy will be evaluated based on the change from Baseline in PANSS negative subscale score after 12 weeks of treatment or at early withdrawal. In addition, other efficacy evaluations will be based on the change from Baseline in the scores on the PSP, and CGI-S Scales, cognitive assessment, CDSS,

The following efficacy evaluations will be performed at the scheduled visits in the following order and in the morning (between 8:00 a.m. to 1:00 p.m.) during the 12-week, double-blind treatment phase, and as applicable, during the 40-week, open-label extension phase:

- at Screening, Baseline, and Weeks 2, 4, 8, 12, and at Weeks 14, 16, 24, 32, 40, 48, 52, and 54 (EOS, or early withdrawal).
- PSP at Baseline and Weeks 4, 8, 12, and at Weeks 16, 24, 32, 40, 48, and 52 (or early withdrawal).
- CGI-S at Screening, Baseline, and Weeks 2, 4, 8, 12, and at Weeks 14, 16, 20, 24, 28, 32, 36, 40, 44, 48, 52, and 54 (EOS, or early withdrawal).
- at Weeks 2, 4, 8, 12, and at Weeks 14, 16, 20, 24, 28, 32, 36, 40, 44, 48, 52, and 54 (EOS, or early withdrawal).
- Cognitive assessments at Baseline and Weeks 4, 12, and at Weeks 16, 24, 36, and 52 (or early withdrawal).
- at Screening, Baseline, and Weeks 4, 8, 12, and at Weeks 16, 24, 36, and 52 (or early withdrawal).

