## 10.5.1. Primary Endpoint

The primary efficacy endpoint will be the change in the NSFS from baseline to Week 12 (the double-blind treatment period). This endpoint will be analyzed using MMRM with treatment arm (MIN-101 64 mg, MIN-101 32 mg, and placebo), pooled study center (by country or region based on enrollment), visit, and treatment arm-by-visit interaction as fixed effects, patient nested in treatment as random effect, and Baseline NSFS as covariate. An unstructured covariance matrix will be used to model the covariance of within-patient scores. The Kenward-Roger approximation (Kenward & Roger 1997) will be used to estimate denominator degrees of freedom. These analyses will be performed based on all post-Baseline scores using only the observed cases without imputation of missing values. Comparison against placebo will be performed with the MIN-101 64 mg and 32 mg doses.

The adjustment for multiplicity within the family of primary hypotheses will utilize the conventional Hochberg procedure for the purpose of reporting of results. This procedure will allow the null hypothesis of no treatment difference for both the 64 mg and 32 mg doses versus placebo to be rejected if largest p-value of comparing either of these 2 doses versus placebo is at or below 0.050. Otherwise, the lowest of these 2 p-values must be at or below 0.025 to allow for rejecting the null hypothesis for the representative dose.

The overall type I error rate for testing the 2 MIN-101 doses versus placebo for the primary and the key secondary endpoint will be controlled at the 2-sided 0.05 level. The primary family of hypotheses (corresponding to the primary endpoint) and the secondary family of hypotheses (corresponding to the key secondary endpoint, the change from Baseline in PSP Total score) will be tested in a sequential manner with suitable adjustment for multiplicity within the family of primary hypotheses and within the family of the secondary hypotheses such that a MIN-101 dose versus placebo null hypothesis contrast testing within the secondary family can be evaluated only when the same null hypothesis contrast in the primary family was rejected.

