## 5.2.5. Key Secondary Efficacy Analysis

As noted in Section 3.3.4, no imputation of data elements will be performed for the key secondary analysis to be submitted to the US FDA. Pattern-mixture modelling imputation of missing key secondary endpoint data will be performed before conducting the key secondary endpoint analysis to submit within the EMA dossier. In both approaches, the estimand and analytic approach of using MMRM to evaluate the potential treatment effects is the same, but the data used to analyze the estimand is different between the US FDA and EMA dossiers.

The Personal and Social Performance (PSP) total score and change from Baseline will be summarized by treatment group and study visit. In addition, the trend in change from Baseline in PSP total score over the series of visit assessments will be presented graphically.

Change from Baseline to Week 12 in the PSP total score will be analyzed using a MMRM with fixed effects for treatment group (MIN-101 64 mg, MIN-101 32 mg, and placebo), region, visit, and treatment-by-visit interaction, a random effect for patient within treatment group, and Baseline PSP total score as covariate. An unstructured covariance matrix will be used to model the covariance of within-patient scores. The Kenward-Roger approximation will be used to estimate denominator degrees of freedom. Comparison against placebo will be performed with the MIN-101 64 mg and 32 mg doses.

As described in Section 3.3.3.2, the change from Baseline to Week 12 in the PSP total score will only be evaluated if both of the primary efficacy comparisons were significant. In this case the adjustment for multiplicity within the family of key secondary hypotheses will utilize the truncated Hochberg procedure for the purpose of reporting results. This procedure will allow the null hypothesis of no treatment difference for both the 64 mg and 32 mg doses versus placebo to be rejected if largest p-value of comparing either of these 2 doses versus placebo is at or below 0.05.

Otherwise, the lowest of these 2 p-values must be at or below 0.025 reject the null hypothesis for the representative dose.

Three approaches will be used to assess the sensitivity of the primary endpoint to patterns of early withdrawals or missing data as described in Section 3.3.4.2. The sensitivity analyses will implement the same analytic approach using MMRM to evaluate potential treatment effects.

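### The MMRM has no Baseline-by-visit term. Adding it costs 2–3 degrees of freedom and protects the observed-case Week 12 contrast if the Baseline slope changes over visits and Baseline-related drop-out differs between arms

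*SAP*

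**What the plan says.** SAP 5.2.2 gives the primary MMRM fixed effects for treatment group, "region, visit, and treatment-by-visit interaction, a random effect for patient within treatment group, and Baseline NSFS as covariate". It adds: "An unstructured covariance matrix will be used to model the covariance of within-patient scores". SAP 5.2.5 repeats the structure for the key secondary endpoint, ending "and Baseline PSP total score as covariate". Protocol 10.5.1 has the same form ("patient nested in treatment as random effect, and Baseline NSFS as covariate"), as does the synopsis. SAP 3.3.1 names Baseline as a covariate and mentions no interaction. SAP 5.2.8 analyses CGI-S with the primary model.

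Protocol 8.2.2 schedules one assessment "at Screening, Baseline, and Weeks 2, 4, 8, 12, and at Weeks 14, 16, 24, 32, 40, 48, 52, and 54". The instrument name is missing there, but the PANSS row of the SAP schedule (1.2) shows the same double-blind visits. It schedules "PSP at Baseline and Weeks 4, 8, 12". NSFS therefore has four scheduled post-Baseline visits and PSP three.

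The estimand (SAP 5.2.1) is the effect if every patient had stayed on the assigned treatment. For the FDA, missing scores are not imputed (SAP 3.3.4).

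**The concern.** Everything in the model may vary by visit except the Baseline slope. With no imputation, the model itself carries the Week 12 information for patients who leave. Many may leave: in the Phase 2b study, 165 of 244 completed the double-blind phase (Protocol 1.4.2, Table 2), so 79/244 = 32% did not.

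If change relates to Baseline more strongly at Week 12 than at Week 2, a common slope is too shallow at Week 12. Should the remaining patients also differ in Baseline between arms, the misfit does not cancel and enters the estimated treatment difference. At stake is a confirmatory contrast that carries an avoidable restriction. Neither document gives a reason for it.

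**Working it through.** **The plan's own figures.** Neither document gives a figure for the Baseline slope. The simulations borrow the SD and the arm size, which reproduce. n = 2(1.960 + 1.282)² × 6.5² / 3² = 98.7, so 99 per arm by normal approximation. The t-based power is 0.898 at 99 and 0.901 at 100. Then 100 / 0.60 = 166.7, so 167, and 3 × 167 = 501.

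**Degrees of freedom.** The term adds (visits − 1) parameters: 4 − 1 = 3 for NSFS and 3 − 1 = 2 for PSP. The two-sided 5% critical t moves from 1.9679 (df 300) to 1.9680 (df 297). SAP 3.3.7 windows early-termination scores by date. If this creates Weeks 1 and 3 for NSFS, or Weeks 1 to 3 for PSP, there are six visits and the cost is 5.

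**Mechanism.** Let β₁₂ be the true Week 12 slope and β the fitted common slope. To first order, an arm's Week 12 mean is misfitted by (β₁₂ − β) × (mean Baseline of those still observed − mean Baseline of the arm). The treatment contrast takes the between-arm difference of this quantity. It is zero if the slopes are equal at all visits, or if drop-out shifts Baseline equally in every arm. Reversing the drop-out pattern reverses the sign.

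**Large-sample simulation.** Three arms of 150,000; no treatment effect; unstructured covariance fitted by maximum likelihood; region omitted. From the plan: Week 12 residual SD 6.5. Assumed: Baseline SD 4, adjacent-visit correlation 0.75, 40% monotone drop-out depending on Baseline only, and the slopes below. g is the log-odds of drop-out per Baseline SD, so g = 0.5 is an odds ratio of 1.65. Mild slopes are −0.10, −0.15, −0.25, −0.30; strong slopes are −0.10, −0.25, −0.45, −0.60.

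Week 12 bias in NSFS points, mean of the two dose contrasts, common slope → with Baseline-by-visit:

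| Drop-out dependence on Baseline | Mild slopes | Strong slopes |
|---|---|---|
| none | −0.04 → −0.04 | 0.02 → 0.02 |
| equal in all arms, g = 1 | −0.05 → −0.04 | −0.02 → −0.01 |
| placebo only, g = 0.5 | −0.13 → −0.01 | −0.29 → 0.02 |
| placebo only, g = 1 | −0.21 → 0.01 | −0.59 → −0.07 |
| +0.5 placebo, −0.5 active | −0.25 → −0.01 | −0.62 → 0.00 |
| +1 placebo, −1 active | −0.42 → 0.00 | −1.08 → −0.01 |

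Simulation noise is about 0.84 × √(167/150,000) = 0.03 per contrast and is largely shared by the two models. With flat slopes (−0.3), both models stayed within 0.05 of zero under every pattern and agreed to within 0.01.

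**Trial size.** With 167 per arm and 700 replicates, type I error per contrast (Monte Carlo error about 0.008), common slope against interaction, was:

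- mild slopes, placebo only, g = 0.5: 0.047 against 0.041;
- mild slopes, +1/−1: 0.077 against 0.043;
- strong slopes, +0.5/−0.5: 0.109 against 0.054;
- equal dependence: 0.039 to 0.064 against 0.041 to 0.063.

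**Precision.** The empirical SD of the contrast went from 0.840 to 0.839 (flat slopes, equal dependence) and from 0.862 to 0.840 (strong slopes, equal dependence). The only increase was 0.828 to 0.850, or 2.7%, with mild slopes and +1/−1. There the common-slope model carried a bias of −0.42.

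**Second simulation.** With 167 per arm, about 34% drop-out, slopes from −0.08 to −0.35 and placebo drop-outs about 1.9 points worse at Baseline, the false effect was −0.14 (Monte Carlo SE 0.02) against 0.01 with the interaction. Weaker dependence or flatter slopes gave −0.08 to −0.10.

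**PSP.** With assumed SDs of 10 and slopes from −0.1 to −0.3, equal dependence gave 0.01 to 0.02. Arm-differential dependence gave −0.3 to −1.2, falling to within 0.1 with the interaction.

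**The case against.** The strongest reply is that the effect is small wherever the assumptions are moderate. In the mild, placebo-only case at trial size, the bias of −0.14 is 0.142/0.852 = 0.17 of a standard error, and type I error hardly moves. The larger figures need either steeply diverging slopes or strong or opposite-signed dependence, which nothing in the documents suggests. The FDA analysis also has three sensitivity analyses that fill in Week 12 and so avoid this mechanism. All of this stands as a limit on size. However, those analyses change the whole treatment of missing data and could not isolate this restriction, and small size is no argument for keeping a restriction that can be removed at almost no cost.

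Four stronger readings are tempting, and the documents do not support them.

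- **Drop-out that depends on Baseline is enough to cause bias.** It is not: equal dependence cancels because randomization balances Baseline.
- **The bias favours MIN-101.** That follows only from assuming that more severe patients leave placebo more often. The Phase 2a relapse figures (25% on placebo, 13% on MIN-101; Protocol 1.4.2.2) concern arm, not Baseline severity within arm. The percentage-based PANSS stopping rule (Protocol 9.3) demands a larger absolute rise from patients with higher totals.
- **The EMA analysis shares the bias.** Missing Week 12 values are imputed there (SAP 3.3.4.1), so Baseline is balanced at Week 12. Any bias would come from the imputation, which this term does not touch.
- **The 40% in the sample-size section is expected Week 12 drop-out.** It is defined there as patients lacking Baseline or any on-treatment assessment. The 40% in the simulation is an assumption of its own.

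**Conclusion.** The point holds as a low-cost improvement. Both confirmatory MMRMs force a single Baseline slope, and in the observed-case analysis this can bias the Week 12 contrast if slopes change over visits and Baseline-related drop-out differs by arm. The size rests on assumed inputs. It is about 0.13 points under mild, placebo-only dependence, which is 0.13/3 = 4% of the planning effect and 7% to 8% of the Phase 2b estimates (0.13/1.97 and 0.13/1.54). It reaches 1.08 points (36% of 3) under the strongest pattern run, and is nil when either condition fails.

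The documents show only that such conditions are possible. Protocol 3.2 describes benefit accumulating over time, and SAP 3.3.4.2.1 contemplates withdrawal timing that differs by arm. Neither says anything about Baseline slopes or Baseline-related drop-out. The direction cannot be stated in advance, and the term gives no protection against drop-out that is not at random.

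**What to change.** Before the double-blind phase is unblinded, add the Baseline-by-visit interaction to the fixed effects, keeping the Baseline main effect, in:

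- SAP 5.2.2 (Baseline NSFS by visit);
- SAP 5.2.5 (Baseline PSP total score by visit);
- Protocol 10.5.1 and the matching synopsis text.

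SAP 5.2.8 follows, because CGI-S uses the same model. If the protocol is no longer being amended, record the change in SAP Section 7. Added after unblinding, the term would look data-driven.

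The cost is one model term per analysis, with the degrees of freedom shown above. No change to data collection or sample size is needed.
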